15.2 Ibrutinib for Oral Administration (Ibruvica™, PCI-32765)

15.21 **Background:** Ibrutinib is a potent and irreversible inhibitor of Bruton's tyrosine kinase (BTK), an integral component of the B-cell receptor (BCR) and cytokine receptor pathways. Constitutive activation of B-cell receptor signaling is important for survival of malignant B-cells; BTK inhibition results in decreased malignant B-cell proliferation and survival.

15.22 **Formulation:** Commercially available for oral administration as a capsule: 70 mg, 140mg (limited availability). Capsules are packaged in aclar blister pack with aluminum lidding foil, or high-density polyethylene bottles with an induction seal and a child resistant screw-top cap. The number of capsules in each aclar blister pack or per bottle is indicated on the label. Commercially available for oral administration as a tablet: 140 mg, 280 mg, 420 mg, and 560 mg.

15.23 **Preparation and storage:** Refer to package insert for complete dispensing instructions. Store capsules and tablets at room temperature between 20°C and 25°C (68°F and 77°F). Excursions are permitted between 15° and 30°C (59°F to 86°F). Keep tablets in original packaging.

15.24 **Administration:** Refer to the treatment section for specific administration instructions. The manufacturer recommends ibrutinib should be taken with water at the same time every day. Ibrutinib can be taken with or without food. The capsules or tablets should be swallowed whole with water followed by a drink of water after swallowing; the capsules should not be opened, broken, or chewed; the tablets should not be broken or chewed.. Ibrutinib should be held at least 3-7 days pre- and post- surgery depending upon the type of surgery and the risk of bleeding. Hazardous agent; use appropriate precautions for handling and disposal.

15.25 **Pharmacokinetic information:**
Distribution: ~10,000 L
Bioavailability: Administration with food increased the maximum concentration by ~2 to 4-fold and the AUC 2-fold (compared with overnight fasting). Administration under fasting conditions resulted in exposure of ~60% compared

to when administered either 30 minutes before or after a meal, or 2 hours after a high-fat meal.

Protein binding: ~97%

Metabolism: Hepatic via CYP3A (major) and CYP2D6 (minor) to active metabolite PCI-45227

Ibrutinib is metabolized in the liver

Time to peak: 1 to 2 hours

Elimination –The excretion of ibrutinib is predominantly via the feces with approximately 80% recovered mostly within 2 days, whereas ~8% is excreted in urine. Approximately 1% of the ibrutinib is recovered as unchanged drug, all in feces. The half-life elimination is 4-6 hours. Overall, these PK characteristics resulted in minimal accumulation of both parent compound and metabolite PCI-45227 on repeated daily dosing of ibrutinib.

Special populations: a small increase in bioavailability was estimated with increasing age. Population PK indicated that in older subjects (67 to 81 years), a 14% higher ibrutinib exposure is predicted. Dose adjustment by age is not warranted. No statistically significant effects were observed for the other covariates tested, i.e., sex, race, mild and moderate renal impairment, mild hepatic impairment and B-cell histology. No dose adjustment is needed for subjects with mild or moderate renal impairment (with creatinine clearance greater than 30 mL/min). Hydration should be maintained, and serum creatinine levels monitored periodically. There are no data in patients with severe renal impairment or patients on dialysis. Monitor patients with liver impairment for signs of ibrutinib toxicity and follow dose modification guidance as needed. For subjects with mild liver impairment (Child-Pugh class A), the recommended dose is 280 mg daily. For subjects with moderate liver impairment (Child-Pugh class B), the recommended dose is 140 mg daily. It is not recommended to administer ibrutinib to subjects with severe hepatic impairment (Child-Pugh Class C).

Patients with cGVHD: The recommended dosage is 140 mg daily for patients 12 years of age and older with total bilirubin level >1.5 to $3 \times$ upper limit of normal (ULN) (unless of non-hepatic origin or due to Gilbert's syndrome). The recommended dosage is 80 mg/m² daily for patients 1 to <12 years of age with total bilirubin level >1.5 to $3 \times$ ULN (unless of non-hepatic origin or due to Gilbert's syndrome). Avoid the use of ibrutinib in these patients with total bilirubin level $>3 \times$ ULN (unless of non-hepatic origin or due to Gilbert's syndrome). Based on pooled population pharmacokinetic analysis in pediatric patients with cGVHD treated with ibrutinib at 240 mg/m² once daily (patients aged ≥ 1 to <12 years) or 420 mg once daily (patients aged ≥ 12 years), exposure in this population was within the exposure range for adult patients with cGVHD. The safety and efficacy of ibrutinib have been evaluated in children aged 1 year and older with previously treated moderate or severe cGVHD. Ibrutinib is not recommended for use in children and adolescents younger than 18 years of age for other indications

15.26 Potential Drug Interactions:

Metabolism Effects: Ibrutinib is primarily metabolized by cytochrome P450 enzyme 3A4/5. Avoid concomitant use of ibrutinib with any of the following: CYP3A4 inducers (strong), CYP3A4 inhibitors (strong or moderate) and herbs that are CYP3A4 inducers or inhibitors. The levels of ibrutinib may be increased by CYP3A4 inhibitors and decreased by CYP3A4 inducers (the active metabolite has inhibitory activity towards Bruton's tyrosine kinase that is approximately 15 times lower than that of ibrutinib).

Transport Effects: Ibrutinib is a P-glycoprotein/ABCB1 inhibitor and may increase the serum concentrations of: afatinib, bosutinib, brentuximab, colchicine, active metabolites of dabigatran etexilate, doxorubicin, edoxaban, everolimus, ledipasvir, naloxegol, pazopanib, prucalopride, rifaximin, rivaroxaban, silodosin, topotecan and vincristine.

Ibrutinib may enhance the adverse/toxic effect of clozapine, leflunomide, natalizumab, pimecrolimus, tofacitinib, tacrolimus, and live vaccines. It may also enhance the adverse/toxic effect of anticoagulants and agents with antiplatelet properties. Dipyrone may enhance the adverse/toxic effect of ibrutinib.

Grapefruit juice and Seville oranges moderately inhibit CYP3A and may increase ibrutinib exposure.

15.27 **Known potential toxicities:** Consult the package insert for the most current and complete information.

Common known potential toxicities, >10%:

Atrial fibrillation

Pyrexia

Dermatologic: Skin rash, skin infection, pruritis

Gastrointestinal: Diarrhea

Hematologic & oncologic: Febrile neutropenia,

Respiratory: pneumonia

Miscellaneous: Fever

Less common/Rare known potential toxicities, 1% - 10%:

leukocytosis, neutropenia, thrombocytopenia, cardiac failure, congestive cardiac failure, ventricular tachycardia, eye hemorrhage, nausea, stomatitis, vomiting, mouth ulceration, peripheral edema, sepsis, cellulitis, urinary tract infection, septic shock, pneumocystis jirovecii pneumonia, bacterial pneumonia, upper respiratory tract infection, bronchopulmonary aspergillosis, neutropenic sepsis, fungal pneumonia, bacteremia, erysipelas, viral pneumonia, skin infection, bacterial sepsis, haemophilus pneumonia, klebsiella pneumonia, sinusitis, staphylococcal bacteremia, staphylococcal sepsis, urosepsis, atypical pneumonia, cellulitis orbital, enterococcal sepsis, Escherichia sepsis, folliculitis, lung abscess, paronychia, pneumonia cytomegaloviral, pneumonia legionella, pneumonia pseudomonas, pulmonary tuberculosis, pseudomonas sepsis, streptococcal bacteremia, staphylococcal skin infection, subdural hematoma, neutrophil count decreased, platelet count decreased, tumor lysis syndrome, myalgia, arthralgia, musculoskeletal pain, basal cell carcinoma, cerebrovascular accident, ischemic stroke, transient ischemic stroke, dizziness, interstitial lung disease, pneumonitis, epistaxis, rash, rash maculopapular, dermatitis bullous, drug eruption, purpura, urticaria, hypertension, hematoma

Cardiac Arrhythmias: Fatal and serious cardiac arrhythmias or cardiac failure have occurred in patients treated with ibrutinib. Patients with significant cardiac comorbidities may be at greater risk of events, including sudden fatal cardiac

events. Atrial fibrillation, atrial flutter ventricular tachyarrhythmia and cardiac failure, have been reported, particularly in subjects with acute infections or cardiac risk factors, including hypertension, diabetes mellitus, and a previous history of cardiac arrhythmia. Appropriate clinical evaluation of cardiac history and function should be performed prior to initiating ibrutinib. Patients should be carefully monitored during treatment for signs of clinical deterioration of cardiac function and clinically managed.

Cerebrovascular accidents: Cases of cerebrovascular accident, transient ischemic attack, and ischemic stroke including fatalities have been reported with the use of ibrutinib in the post-marketing setting, with and without concomitant atrial fibrillation and/or hypertension. Regular monitoring and appropriate treatment of conditions that can contribute to the occurrence of these events is recommended.

Limited to important or life threatening: Dermatologic disorder (neutrophilic dermatosis), abnormal platelet aggregation, hepatic cirrhosis, acute hepatic failure, hypersensitivity (includes anaphylactic shock, angioedema), hyponatremia, interstitial pulmonary disease, onychoclasia, peripheral neuropathy, pneumonia due to *Pneumocystis carinii*, pneumonitis, progressive multifocal leukoencephalopathy, reactivation of HBV, renal failure syndrome, Stevens-Johnson syndrome, tumor lysis syndrome, urticaria

15.28 **Drug procurement:** Commercial supplies. Pharmacies or clinics shall obtain supplies from normal commercial supply chain or wholesaler.

15.29 **Nursing Guidelines:**

1. There are numerous drug to drug interactions. Record all of patient's medications including OTC, and herbal use. Avoid concomitant use with agents as listed in section 15.26.
2. Ibrutinib should be taken with water at approximately the same time each day and can be taken with or without food. Capsules should be swallowed whole.
3. Patients should be instructed to avoid eating grapefruit (including juice) and Seville oranges while on ibrutinib.
4. Peripheral edema is common. Instruct patients to report this to the study team.
5. Gastrointestinal side effects are common (diarrhea, nausea, constipation, abdominal pain, vomiting, etc). Treat symptomatically and monitor for effectiveness of intervention.
6. Monitor CBC w/diff. Instruct patients in energy conserving lifestyle (anemia) and to report any unusual bruising or bleeding and/or signs or symptoms of infection to study team.
7. Arthralgias, myalgias, and muscle spasm can be seen. Treat symptomatically and monitor for effectiveness.
8. Monitor renal function/uric acid levels, especially in patients who may be experiencing dehydration.
9. Respiratory symptoms may include, cough, SOB, and URI. Instruct patients to report these symptoms to the study team.
10. Rarely patients can experience secondary skin cancers. Instruct patients to report any new skin lesions to the study team.
11. Rash can be seen. Instruct patient to report to study team.

12. Cardiac arrhythmias have been seen with this agent including a-fib, atrial flutter and ventricular tachyarrhythmia's, some of which have led to death. Instruct patients who experience any palpitations, lightheadedness, syncope, or SOB to see medical care immediately. This is especially important in patients who have pre-existing cardiac issues.
13. Warn patients of the risk of bleeding. Patients should not take warfarin or other vitamin K antagonists while on ibrutinib, unless the protocol allows for it. Additionally, patients should be cautioned to avoid fish oil and Vitamin E supplements.
14. Patients who are concurrently on ibrutinib and venetoclax should be monitored closely for excess toxicity.
15. Ibrutinib should be held at least 3-7 days pre and post-surgery, depending on type of surgery.
16. There have been reports of CVA and TIA in patients on ibrutinib. Instruct patients to report any headaches and/or neurologic changes immediately or seek out emergency care.
17. Patients may experience dry eyes, blurred vision or decreases in vision. Instruct patients to report this to the study team.

16.0 Statistical Considerations and Methodology

16.1 Overview:

This is a Phase II study designed to assess the overall response rate of daratumumab and ibrutinib for relapsed/refractory CLL in two groups independently: Previously received Ibrutinib (Cohort 1) and Ibrutinib naïve (Cohort 2).

16.11 Primary Endpoint:

The primary endpoint in each cohort is the overall response rate after 6 cycles of treatment with daratumumab in combination with ibrutinib (end of Cycle 7). All patients meeting the eligibility criteria who have signed a consent form and have begun treatment will be evaluable for overall response, with the exception of patients who are determined to be a major treatment schedule violation.

16.12 Sample Size:

The phase II study design to be used in each group is fully described in section 16.2. A maximum of 22 evaluable Cohort 1 and 26 evaluable Cohort 2 patients will be accrued unless undue toxicity is encountered. We anticipate accruing an additional 4 patients (2 Cohort 1, 2 Cohort 2) to account for ineligibility, cancellation, major treatment violation, or other reasons. Maximum projected accrual is 52 patients overall.

16.13 Accrual Rate and Study Duration:

The anticipated accrual rate is approximately 2-3 patients per month. Therefore, the accrual period for this phase II study is expected to be about 2 years. The maximum total study duration is expected to be approximately 7 years, or until the last patient accrued has been observed for at least 5 years. The earliest date anticipated for presentation of results is at approximately 2.5 years, or when the last patient accrued has completed the cycle 7 response assessment.

16.2 Statistical Design:

16.21 Decision Rule for previously received Ibrutinib group (Cohort 1)

Since patients in this group have been previously treated with Ibrutinib, the patients may have a plateaued response to ibrutinib. A response rate of at least 20% with the addition of daratumumab to ibrutinib would be of interest.

The largest success proportion where the proposed treatment regimen would be considered ineffective in this population is 5%, representing a response by chance alone. The smallest success proportion that would warrant subsequent studies with the proposed regimen in this patient population is 20%. The following one-stage binomial design uses 22 evaluable patients to test the null hypothesis that the true success proportion in a given patient population is at most 5%.

16.211 Final Decision Rule

Enter 22 evaluable patients into the study. If 2 or fewer successes are observed in the first 22 evaluable patients, we will consider this regimen ineffective in this patient population and terminate this study. Otherwise, if the number of successes is at least 3, this will be considered evidence of promising activity and the treatment may be recommended for further testing in subsequent studies.

16.212 Power and Significance Level

Assuming that the number of responses is binomially distributed, with a significance level of 9%, the probability of declaring that the regimen warrants further studies (i.e., statistical power) can be tabulated as a function of the true success proportion as shown in the table below.

If the true success proportion is...	0.05	0.10	0.15	0.20
Then the probability of declaring that the regimen is promising and warrants further study is...	0.09	0.38	0.66	0.85

16.22 Decision Rule for Ibrutinib naïve group (Cohort 2):

In a previous study including 85 patients with relapsed/refractory CLL treated with single agent ibrutinib, the overall response rate at 8 months was 54%. The overall response rate was the same regardless of dose level received (51 patients received 420 mg and 34 received 840 mg). An increase in overall response rate after 8 months of treatment with the combination of daratumumab and 420 mg of ibrutinib would be of interest.

The largest success proportion where the proposed treatment regimen would be considered ineffective in this population is 50%, and the smallest success proportion that would warrant subsequent studies with the proposed regimen in this patient population is 75%. The following one-stage binomial design uses 26 evaluable patients to test the null hypothesis that the true success proportion in a given patient population is at most 50%.

16.221 Final Decision Rule: Enter 26 evaluable patients into the study. If 16 or fewer successes are observed in the first 26 evaluable patients, we will consider this regimen ineffective in this patient population and terminate this study. Otherwise, if the number of successes is at least 17, this will be considered evidence of promising activity and the treatment may be recommended for further testing in subsequent studies.

16.222 Power and Significance Level: Assuming that the number of responses is binomially distributed, with a significance level of 8%, the probability of declaring that the regimen warrants further studies (i.e., statistical power) can be tabulated as a function of the true success proportion as shown in the table below.

If the true success proportion is...	0.50	0.55	0.60	0.65	0.70	0.75
Then the probability of declaring that the regimen is promising and warrants further study is...	0.08	0.19	0.36	0.57	0.77	0.91

16.23 Other Considerations: Toxicity, quality/duration of response, and patterns of treatment failure observed in this study, as well as scientific discoveries or changes in standard care will be taken into account in any decision to terminate the study.

16.24 Over Accrual: If more than the target number of patients are accrued, then the

additional patients will not be used to evaluate the stopping rule or used in any decision making process. Analyses involving over accrued patients are discussed in Section 16.34.

16.3 Analysis Plan

The analysis for this trial will commence at planned time points (see 16.2) and at the time the patients have become evaluable for the primary endpoint. Such a decision will be made by the Statistician and Study Chair in accordance with CCS Standard Operating Procedures, availability of data for secondary endpoints (e.g., laboratory correlates), and the level of data maturity. It is anticipated that the earliest date in which the results will be made available via manuscript, abstract, or presentation format is when the last patient has been followed for at least 6 cycles of combination treatment (7 cycles total).

16.31 **Primary Endpoint (to be evaluated in each cohort independently)**

16.311 **Definition:** The primary endpoint in each cohort is the overall response rate after 6 cycles of treatment with daratumumab in combination with ibrutinib. A response is defined as an objective status of CR, CRi, CCR, nPR, or PR after 6 cycles of combination treatment (end of cycle 6). All patients meeting the eligibility criteria who have signed a consent form and have begun treatment will be evaluable for response, with the exception of patients who are determined to be a major treatment schedule violation.

16.312 **Estimation:** In each cohort, the proportion of successes will be estimated by the number of successes divided by the total number of evaluable patients. Ninety- five percent exact binomial confidence intervals for the true success proportion will be calculated.

16.32 **Secondary Endpoints (to be evaluated in each cohort independently)**

16.321 The best overall response rate at any time during the course of treatment with daratumumab plus ibrutinib will be estimated by the number of patients who achieve a CR, CRi, CCR, nPR, or PR at any time during combination treatment divided by the total number of evaluable patients. Exact binomial 95% confidence intervals for the true success rate will be calculated.

16.322 The MRD response rate at any time during the course of treatment with daratumumab plus ibrutinib will be estimated by the number of patients who achieve MRD negative response in both blood and bone marrow at any time during combination treatment divided by the total number of evaluable patients. Exact binomial 95% confidence intervals for the true success rate will be calculated. In patients who achieve MRD negative response, time to achieve MRD negative response will be summarized descriptively (median, range). Time to achieve MRD negative response is defined as time from registration to the earliest date of documentation of MRD negative response in both blood and bone marrow.

16.323 Progression-free survival is defined as the time from registration to the earliest date of documentation of disease progression or death due to any cause. Patients who receive subsequent treatment for CLL before disease progression will be censored on the date of their last disease assessment prior to initiation of the subsequent treatment. The distribution of progression-free survival will be

estimated using the method of Kaplan-Meier.

16.324 Adverse Events: Platelets and hemoglobin will be graded according to the Grading Scale for Hematologic Adverse Events in CLL Studies in Appendix V. The maximum grade for each type of adverse event, regardless of causality, will be recorded and reported for each patient, and frequency tables will be reviewed to determine adverse event patterns. Adverse events will continue to be recorded and reported up to 30 days after the last day of study drug treatment.

16.34 Over Accrual: If more than the target number of patients are accrued, then the additional patients will not be used to evaluate the stopping rule or used in any decision making processes; however, they will be included in final point estimates and confidence intervals.

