Overall design: This is a phase II clinical trial of two novel drugs (daratumumab and hyaluronidase given SC and ibrutinib given orally) for treatment of patients with relapsed or refractory CLL. During the first cycle of the treatment, patients are given daratumumab as a single agent (for conduct of correlative studies – please see section 7.0), and starting cycle 2 patients will have both ibrutinib and daratumumab given together. Patients will be grouped in independent cohorts based upon whether they previously received a BTK inhibitor (Cohort 1) vs. BTK inhibitor naïve (Cohort 2). A total of 52 eligible patients will be enrolled in two separate cohorts (i.e. Cohort 1 and 2). A total of 25 cycles (including the first cycle with single agent daratumumab) will be given. The primary goal is to determine ORR of this regimen in each arm.

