7.0 Protocol Treatment

Overall Treatment Schedule: Overall treatment schedule (for both Cohorts) include patient receiving Daratumumab SC alone in C1 followed by addition of ibrutinib to daratumumab starting C2 (and onwards). For patients already on BTK inhibitor who are entering Cohort 1, BTK inhibitor will be stopped (see also note below for more detailed clarification) for at least 1 week prior (washout period) to initiating C1 (daratumumab alone). Once these patients have completed the C1, ibrutinib will be started as part of the combination regimen starting C2.

Note: Treatment can be initiated/continued independent of disease activity during the washout period i.e. if the disease is progressing while on Daratumumab alone. Also, given the clinical course of patients resistant to BTK inhibitor can be rapid, if in treating physician opinion stopping the BTK inhibitor can impact adversely patient's disease course than patient may continue the BTK inhibitor up until starting study treatment and then Ibrutinib plus daratumumab will be started in lieu of BTK inhibitor. In such a case, Cycle 1 will have both ibrutinib + Daratumumab. The schedule and dosing of Daratumumab will follow the same design as noted in 7.2. This, however must be approved by the Principal Investigator [REDACTED] of the study protocol.

Duration of treatment: Patient will be treated as indicated in section 7.0, unless they have progressive disease or unacceptable toxicity. Patients who complete treatment per protocol will continue to the end of treatment visit and then, survival follow-up.

DARATUMUMAB

7.1 Daratumumab Subcutaneous schedule (Cycle length = 28 days, ± 4 days):

- **Cycle 1 & 2:** Daratumumab SC alone (1800 mg dose) weekly (Days 1, 8, 15, 22 of each cycle).
- **Cycle 3-6:** Daratumumab SC (1800 mg dose) will be given every 2 weeks (Days 1, 15 of each cycle).
- **Cycle 7 onwards:** Daratumumab SC (1800 mg dose) will be given every 4 weeks (Day 1 of each cycle).

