16.4 Results Reporting on ClinicalTrials.gov

At study activation, this study will have been registered within the [REDACTED] website. The Primary and Secondary Endpoints along with other required information for this study will be reported on [REDACTED]. For purposes of timing of the Results Reporting, the initial estimated completion date for the Primary Endpoint of this study is 2.5 years after the study opens to accrual. The definition of "Primary Endpoint Completion Date" (PECD) for this study is at the time all patients registered have completed the cycle 7 response assessment (or discontinued treatment before completion of 7 cycles of treatment)..

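### Section 16.311 times the primary response at the end of Cycle 6, but with the daratumumab lead-in six combination cycles end at Cycle 7, and no formal response evaluation falls at Cycle 6

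*Combined protocol and SAP*

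**What the plan says.** The primary endpoint is defined twice in the statistical section. Section 16.11 places it after six cycles of treatment with "daratumumab in combination with ibrutinib (end of Cycle 7"). Section 16.311, which lists the response categories that count as a success, places it at CR, CRi, CCR, "nPR, or PR after 6 cycles of combination treatment (end of cycle 6").

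Three further statements bear on the timing:

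- Section 16.3 expects results once the last patient has been "followed for at least 6 cycles of combination treatment (7 cycles total").
- Section 16.13 dates the first presentation of results at about 2.5 years, or "when the last patient accrued has completed the cycle 7 response assessment".
- Section 16.4 sets the primary endpoint completion date "at the time all patients registered have completed the cycle 7 response assessment", or when they have stopped treatment earlier.

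Section 7.0 gives the default schedule for both cohorts: "Daratumumab SC alone in C1 followed by addition of ibrutinib to daratumumab starting C2 (and onwards"). Its note allows an exception, with the principal investigator's approval, for patients for whom stopping a BTK inhibitor is judged harmful: "In such a case, Cycle 1 will have both ibrutinib + Daratumumab". The overall design paragraph in Section 1.3 counts the lead-in as a cycle: "A total of 25 cycles (including the first cycle with single agent daratumumab) will be given".

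Formal response evaluation takes place at the end of Cycle 1. After that it is every 3 combination cycles in Section 4.1 (footnote 2), 11.0 and 11.1(a), but every 2 cycles in Section 7.9b and the note to 11.25. Sections 11.0 and 11.25 say that in all other cycles the patient is recorded only as progressed or not progressed.

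**The concern.** Section 16.311 decides what counts as a success in both decision rules: at least 3 of 22 in Cohort 1 and at least 17 of 26 in Cohort 2. For a patient on the default schedule, its two statements of time cannot both be true: six combination cycles have not been completed by the end of Cycle 6.

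Applied literally, the Cycle 6 label sends the analyst to a visit at which the plan schedules no CR, CRi, CCR, nPR or PR classification. Someone would then have to choose between the Cycle 7 evaluation, an earlier evaluation, and a status rebuilt from the examination and blood counts. Both rules are single-stage with a fixed cut-off, so one patient classified differently at the boundary reverses the conclusion for that cohort. That choice should not be left until the data are in view.

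**Working it through.** **Inputs.** Cycle length is 28 days, ±4 (Sections 7.1 and 7.9d; the nominal 28 is used here). The lead-in is one cycle by default and none under the Section 7.0 note. The evaluation intervals are those listed above. The decision rules come from Sections 16.21 and 16.22.

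**Step 1. The plan's own figures.** The probability of declaring the regimen promising is P(X ≥ r) for X ~ Binomial(n, p).

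| Cohort | n, r | p | Computed | Plan |
|---|---|---|---|---|
| 1 | 22, 3 | 0.05 | 0.0948 | 0.09 |
| 1 | 22, 3 | 0.20 | 0.8455 | 0.85 |
| 2 | 26, 17 | 0.50 | 0.0843 | 0.08 |
| 2 | 26, 17 | 0.75 | 0.9091 | 0.91 |

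The intermediate entries in both tables also match at the printed precision. The design arithmetic is sound, and nothing in it depends on which cycle is meant.

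**Step 2. Combination exposure at each label.** Combination cycles completed at the end of Cycle c = c − L, where L = 1 with the lead-in and L = 0 without it.

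| Group | End of Cycle 6 | End of Cycle 7 |
|---|---|---|
| Lead-in (default) | 6 − 1 = 5 cycles; 5 × 28 = 140 days (20 weeks) | 7 − 1 = 6 cycles; 6 × 28 = 168 days (24 weeks) |
| Both drugs from Cycle 1 (Cohort 1 exception) | 6 cycles; 6 × 28 = 168 days (24 weeks) | 7 cycles; 7 × 28 = 196 days (28 weeks) |

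For the lead-in group only Cycle 7 meets the six-cycle definition. For the exception group only Cycle 6 does.

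**Step 3. Is there a formal evaluation at that visit?** For lead-in patients:

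- Every 3 combination cycles after Cycle 1 (1 + 3k): Cycles 1, 4, 7, 10.
- Every 2 combination cycles after Cycle 1 (1 + 2k): Cycles 1, 3, 5, 7, 9.

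Cycle 7 is on both lists and Cycle 6 on neither. The MRD calendar in Section 4.1, footnote 7 (every 3 cycles, starting at the end of Cycle 4), follows the first count.

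For exception patients the answer depends on where counting starts, which the plan does not say. Counted from the start of the combination, the visits are Cycles 3, 6, 9 or Cycles 2, 4, 6, 8, and both include Cycle 6. Counted after a Cycle 1 evaluation, as for lead-in patients, neither includes it.

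**Step 4. What would be on file at Cycle 6 for a lead-in patient.** The most recent formal status would come from Cycle 4 (3 × 28 = 84 days, 12 weeks of combination) on the 3-cycle interval, or Cycle 5 (4 × 28 = 112 days, 16 weeks) on the 2-cycle interval. The intended exposure is 24 weeks.

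**The case against.** The strongest reply is that the governing words of Section 16.311 are six cycles of combination treatment, that the parenthesis is only a gloss, and that Cycle 6 could be read as the sixth combination cycle. Other text points to the right visit: Section 11.1(a) wants best response documented once six combination cycles are complete, and Section 7.9a refers to response status at the end of Cycle 7. The test schedule also requires a physical examination with tumour measurement and a blood count before each cycle, so a status at Cycle 6 might be rebuilt. The opening sentence of Section 11.0, read alone, would give evaluations at Cycles 3 and 6. Finally, of the four statements that point to Cycle 7, only Section 16.11 defines the endpoint; the others set reporting dates.

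Part of this stands. The intended visit is recoverable, and the plan prescribes no carry-forward, so the 12-week and 16-week figures show what would be on file, not what the plan instructs. A reporting date that waits for Cycle 7 does not in itself move the endpoint of an exception patient.

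The rest does not remove the conflict. The plan numbers the lead-in as the first cycle, and where it counts combination cycles separately, as in Section 13.8, it says so. Even on the charitable reading, one endpoint carries two cycle labels. The sentences that follow the opening of Section 11.0 fix the calendar at Cycle 1 and then every 3 combination cycles. A status rebuilt from raw measurements is not a planned classification. The references in Sections 11.1(a) and 7.9a confirm that Cycle 6 is the wrong label for lead-in patients.

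**Conclusion.** The concern holds. For every patient on the default schedule, Section 16.311 names a visit one cycle (28 days) too early, after five combination cycles instead of six. Scheduled formal evaluations at that visit number zero under either interval, against one at Cycle 7 under each. For Cohort 1 patients who start both drugs in Cycle 1 the Cycle 6 label is correct, and the Cycle 7 label in Section 16.11 would put them one combination cycle too late.

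This rests on nominal 28-day cycles and on the evaluation calendar being counted from Cycle 1 as Sections 11.0 and 11.1(a) describe. A patient who stops treatment near Cycle 6 would have an end-of-treatment evaluation, but that is not a scheduled Cycle 6 assessment. No loss of power is claimed: the documents give no response rates by cycle, and the design figures are unchanged. The eight-month time frame in Section 16.22 is a separate matter and is not relied on here. This is a wording error, but it sits in the operative definition of the primary endpoint and should be corrected before responses are counted.

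**What to change.** 1. In Section 16.311, replace the parenthesis with: at the formal response evaluation after the sixth combination cycle (end of Cycle 7 for patients with the daratumumab lead-in; end of Cycle 6 for Cohort 1 patients who start both drugs in Cycle 1 under the Section 7.0 note). A bare change to Cycle 7 would mistime the second group.
2. Bring the Cycle 7 labels in Sections 16.11, 16.13 and 16.4, and the seven-cycle total in Section 16.3, into line with that wording.
3. Reconcile Section 4.1 (footnote 2) and Sections 7.9b, 11.0, 11.1 and 11.25 to a single response-evaluation interval, and state the cycle from which it is counted, so that both groups have a formal evaluation at their endpoint visit.

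The cost is wording only: one parenthesis, matching labels in four other statements, and one interval stated consistently in five places. Sample size, cut-offs, significance levels and power stay as they are.
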